## 10.5 POOLING OF SITES

Sites will be pooled for all analyses. There will be no adjustment for centre effect or treatment by centre interaction.

## 10.6 MULTIPLE COMPARISONS

Not applicable.

## 10.7 SUBGROUP ANALYSES

The efficacy variables will be presented according to the following subgroups:

- Patients being in clinical response at BOLS
- Patients not being in clinical response at BOLS
- Patients previously treated with biological drugs
- Patients naive from biological drugs

## 10.8 STATISTICAL ISSUES

Not applicable.

# 11 STATISTICAL OUTPUT

General principles for layout of the statistical output are described in Section 10.1, including specification of the table columns, and these are illustrated for each unique table in the table shells in Section 15. For clarity and brevity in this document the phrase “by treatment group” is understood for all summaries and is not included within the text of this section.

## 11.1 PATIENT DISPOSITION

The patient disposition table (*Table 14.1.1*) will summarise the following data for all enrolled patients:

- The number (%) of patients in the OC Set
- The number (%) of patients in the NRI Set

The number (%) of patients who withdraw from the study and the main reason for withdrawal will be summarised for all enrolled patients (*Table 14.1.2*).

A data listing presenting the eligibility for the analysis sets for each patient will be presented.

## 11.2 PATIENT CHARACTERISTICS AT BASELINE

### 11.2.1 Demographic and Baseline Characteristics

Demographics and other baseline characteristics will be summarized by treatment group (*Table 14.1.3*). This analysis will be conducted on the OC Set.

Age will be calculated using Year of Birth and Date of first treatment and presented as age at last birthday as an integer.

Body Mass Index (BMI) is the patient's body weight in kilograms divided by the square of the patient's height in metres.

Age, gender, childbearing potential, race, height, weight and BMI will be summarised using the OC Set.

In addition to demographic and baseline characteristics, disease characteristics (at Day 0) including Total and Modified Mayo score (TMS and MMS), faecal calprotectin, percentage of subjects with concomitant Corticosteroid, clinical remission, corticosteroid-free clinical remission, clinical response, endoscopic remission, endoscopic improvement will also be summarized using the OC Set.

Clinical remission, corticosteroid-free clinical remission, clinical response, endoscopic remission and endoscopic improvement are defined in Section 11.3.1.6 and 11.3.1.7.

### 11.2.2 Medical History and Current Medical Conditions

All conditions will be coded using the version of the Medical Dictionary for regulatory Activities (MedDRA) defined in the Data Management Plan. Past medical/surgical history and current medical conditions will be summarised by system organ class (SOC) and preferred term (PT). The number (%) of patients reporting each condition will be presented using the OC Set (*Table 14.1.4.1* and *14.1.4.2*).

All medical history will be listed.

### 11.2.3 Procedures/ Non-Drug Therapies

All procedures/non-drug therapies recorded on the eCRF will be listed only.

## 11.3 EFFICACY ANALYSES

All efficacy analysis will be conducted on both OC Set and NRI Set except if otherwise specified and will be summarized based on the following subgroups:

- Patients being in clinical response at BOLS and not being in clinical response at BOLS
- Patients previously treated with biological drugs and naive from biological drugs.

Descriptive statistics will be presented by treatment group and include:

- Quantitative variables: n, mean, SD, minimum and maximum, 95% CI, median and quartiles will be presented when considered relevant. Number of missing values will also be presented.
- Qualitative variables: count and percentage. Number of missing values will also be presented.

Listings showing patients efficacy derivations for Mayo Scores, time to UC worsening and SF-36 Questionnaire will be produced for the efficacy endpoints. All efficacy data will be listed.

If a scheduled endoscopic assessment is not performed, then results from the closest unscheduled assessment within 1 month should be used if available.

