5.2.5. M48 (Calendar month ± 14 days)

Visit M48 is the last visit in this study before entering the long-term follow-up study ABX464-108. If the patient is not eligible to enter this ABX464-108 study, she/he will perform the End of Study Visit (EoS) 4 weeks after last study drug intake.

The following examinations/procedures should be performed:

- Physical examination and vital signs;
- Body weight;
- Hematology and Biochemistry including blood pregnancy test for all women of childbearing potential and NT-proBNP;
- Faecal calprotectin dosage;
- 12 leads ECG;
- Blood sampling for miR-124 expression
- Partial Mayo Score;
- Total mayo score;
- Adverse Events and Concomitant Medications reporting;
- Sigmoidoscopy, mandatory;
- Echocardiography
- Schedule the EoS visit (if patient doesn't enter the study ABX464-108)

Nota bene:

- **The last treatment intake in study ABX464-102 should be the day before this visit M48.**
- **The local reading result of sigmoidoscopy need to be available on M48 visit to check eligibility to enter study ABX464-108.** The sigmoidoscopy can be performed within 14 days before the visit but not after the visit. If the sigmoidoscopy results (local reading) are not available on M48, the patient will be considered not eligible to enter the ABX464-108 study and will performed the end of study visit 28 days (+4 days) after M48.

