5.2.6. End of Study Visits

This EoS visit should be performed 28 days (+4 days) after the last study treatment dosing, or if a subject meets a discontinuation criterion before. From the last dosing day, subjects will be treated according to standard of care.

Following examinations/procedures should be performed:

- Physical examination and vital signs;
- Body weight;
- Hematology and Biochemistry including blood pregnancy test for all women of childbearing potential and NT-proBNP;
- Partial Mayo Score;
- 12 leads ECG;
- Faecal calprotectin dosage;
- Adverse Events and Concomitant Medications reporting.

NB: In case of premature discontinuation occurring during the treatment phase the above examinations should be performed as an End of Study Visit 4 weeks after treatment interruption.

After the end of study visit, patients will be treated according to the local standard of care.

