5.3.9. Sigmoidoscopy

A Sigmoidoscopy will be performed in all subjects at Day 56/M2, Month 24, Month 36, and Month 48 (i.e. Study procedure).

In addition, monthly sigmoidoscopies could be performed if deemed necessary by the investigator (Until month 24). In such a case, the endoscopy rating will be reported in the eCRF (Total MCS).

Sigmoidoscopies procedures (or colonoscopies if applicable) at Month 24, Month 36, and Month 48 will be standardized for optimized video acquisition at clinical sites. Sigmoidoscopies should be performed according to the Central Imaging Management System Charter. Central Imaging Management System will be provided including a central image database. Once uploaded, video data will be analyzed for quality and resolution prior to independent review by an expert central reader. Study videos will be scored separately using the Mayo Clinic Score (excluding friability) for all time points by central readers.

The local reading result of sigmoidoscopy need to be available on M48 visit to check eligibility to enter study ABX464-108. The sigmoidoscopy can be performed within 14 days before the visit but not after the visit. If the sigmoidoscopy results (local reading) are not available on M48, the patient will be considered not eligible to enter the ABX464-108 study and will performed the end of study visit 28 days (+4 days) after M48.

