6.3. Administration and Dosing

6.3.1. Administration of the investigational product

Subjects will be dosed with a daily dose of 50 mg that is 1 capsule every day.

Subjects will be orally dosed in fed condition (regular breakfast) with a cup of water.

A subject diary, in which the subject should report the number of capsules taken and the intake time, will be given to the subject at baseline. Moreover, this diary will enable the subject to report also potential discomfort or side effects s/he could experience.

The last study treatment intake should be the day before M48 visit.

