### 11.3.1.6 Clinical remission, corticosteroid-free clinical remission and clinical response

**Clinical remission** is achieved when all the following criteria are met in the components of the Mayo Score:

- rectal bleeding sub-score = 0
- central or local endoscopy sub-score <= 1
- stool frequency sub-score <= 1.

**Corticosteroid-free clinical remission** is defined as clinical remission and concomitant corticosteroid free for  $\geq$  90 days prior to these timepoints among patients with clinical remission after 8 weeks of induction treatment (at baseline of ABX464-102 study).

**Clinical response** is defined as:

- reduction in Modified Mayo Score of at least 2 points and  $\geq$  30 percent from BIS
- with an accompanying decrease in rectal bleeding sub-score of  $\geq$  1 point or absolute rectal bleeding sub-score of  $\leq$  1 point.

Proportion of patients (n and percentage) will be presented for patients achieving clinical remission, corticosteroid-free clinical remission and clinical response at M12, M24, M36 and M48 (*Table 14.2.5.1 and 14.2.5.2*).

In addition, shift tables will be presented showing changes from BIS to each post baseline visit and from BOLS to each post baseline visit (*Table 14.2.5.3 and 14.2.5.4*) for clinical remission.

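### SAP 11.3 lets a missed M48 endoscopy be replaced by one done after ABX464 has stopped, because the substitution rule has no direction and no on-treatment condition

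*SAP*

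**What the plan says.** The SAP has one sentence on a missed endoscopy, in section 11.3: "If a scheduled endoscopic assessment is not performed, then results from the closest unscheduled assessment within 1 month should be used if available". It does not say whether the substitute may fall after the scheduled visit, whether the patient must still be taking ABX464, or whether M48 is treated differently. The length of a month is not defined.

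The protocol fixes what happens around M48:

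- Timing of the M48 endoscopy (5.3.9, repeated in 5.2.5): "The sigmoidoscopy can be performed within 14 days before the visit but not after the visit".
- Last dose (5.2.5): "The last treatment intake in study ABX464-102 should be the day before this visit M48". Section 6.3.1 says the same.
- No local reading at the visit (5.3.9): "If the sigmoidoscopy results (local reading) are not available on M48, the patient will be considered not eligible to enter the ABX464-108 study".
- Care afterwards (5.2.6): "From the last dosing day, subjects will be treated according to standard of care".

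In SAP 11.3.1.6, clinical remission accepts "central or local endoscopy sub-score <= 1". In SAP 11.3.1.7, endoscopic improvement and endoscopic remission use the central reading only. Under SAP 6.2, a missing dichotomous result counts as non-response in the NRI Set. Under SAP 6.1, it stays missing in the OC Set.

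**The concern.** The M48 rates are meant to describe patients after 48 months on ABX464. The patients for whom the substitution rule is triggered at M48 are those with no M48 endoscopy, and the protocol routes them off the drug. Their stool frequency and rectal bleeding scores come from the visit, one day after the last dose. A substitute endoscopy from the following weeks would come from a patient who has stopped ABX464 and may have started another treatment. The composite would then join two treatment states under one M48 label.

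The rule also takes precedence over NRI. Without a substitute the patient is a non-responder in the NRI Set. With one, the patient can be counted as a remitter on an endoscopy that does not reflect current ABX464 treatment. Both analysis sets use the rule, so comparing them would not reveal it. Listing 16.2.6.1 marks visits outside the window but carries neither the endoscopy date nor a substitution flag.

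**Working it through.** The plan gives no figure to reproduce on this point (sample size is stated as not applicable), so the check uses date arithmetic and the table denominators.

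**Inputs**

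- Substitution limit: 1 month (SAP 11.3). Assumed to be m = 28, 30 or 31 days.
- Last dose: day -1 relative to M48 (Protocol 5.2.5, 6.3.1).
- Protocol window for the M48 endoscopy: day -14 to day 0, which is 15 days (Protocol 5.2.5, 5.3.9).
- Half-life of the active metabolite ABX464-N-Glu: about 100 hours (Protocol 1.2.5).
- Enrolled: 22, of whom 15 previously received ABX464 and 7 placebo (Protocol 1.3). All 22 are assumed to have been dosed and so to be in the OC Set.

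**Step 1. Time off drug.** Days since last dose = days after M48 + 1. At the far end of the window this is 28 + 1 = 29, 30 + 1 = 31 or 31 + 1 = 32 days. For an endoscopy on the visit day it is 1 day.

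**Step 2. Share of the window after the visit.** Read on both sides, the SAP window is 2m + 1 = 57, 61 or 63 days. The part after M48 is m/(2m + 1) = 28/57, 30/61 or 31/63, about 49% each time.

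**Step 3. Residual exposure.** Fraction left = 0.5^(24 × days/100). At 29 days: 0.5^6.96 = 0.8%. At 32 days: 0.5^7.68 = 0.5%. It falls below 10% after 100 × log2(10)/24 = 13.8 days. A substitute from the first days after M48 would still carry appreciable exposure. One from the end of the window would carry almost none.

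**Step 4. Endpoints reached.**

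| Endpoint at M48 | Endoscopy reading | Exposure |
|---|---|---|
| Clinical remission (and the corticosteroid-free and sustained versions built on it) | central or local | main exposure |
| Clinical response, through the MMS | not specified for the MMS | possible |
| Endoscopic improvement, endoscopic remission | central only | less |

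An endoscopy done in routine care after M48 would ordinarily have only a local reading, which is why the last row is less exposed.

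**Step 5. Size.** The shells of Tables 14.2.5.1 and 14.2.6.1 set the denominator to the number of patients in the column, with missing as its own row, and the same layouts serve the NRI tables. One patient moved to remission therefore changes the Total column by 1/22 = 4.5 points in either set. The previous-treatment columns move by 1/15 = 6.7 or 1/7 = 14.3 points.

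**Step 6. Direction.** Compared with leaving the assessment missing, a post-visit substitute can only leave the remission count unchanged or raise it. Compared with the on-drug endoscopy that was never done, the direction is not determined: loss of drug could worsen the score and new treatment could improve it.

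**The case against.** The strongest reply is that the scenario has little route in this study. Investigator-discretion sigmoidoscopies are foreseen only until M24. The End of Study visit ("This EoS visit should be performed 28 days (+4 days) after the last study treatment dosing") includes none. A post-M48 endoscopy would have to arise in routine care, be entered in the eCRF, and be the closest one available. This stands, and it is why the point is a cheap improvement and not a serious defect. The study is also open-label and descriptive, with a safety primary endpoint.

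Several stronger readings are tempting, and the documents do not support them:

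- *That the SAP contradicts the protocol's M48 window.* The bar on endoscopy after the visit stands next to the text on eligibility for ABX464-108 and mainly serves that purpose. The SAP sentence is a contingency for when the endoscopy was not done. Both can hold. The off-drug problem follows from the last-dose date, whatever purpose that bar serves.
- *That any endoscopy on either side may be used.* The SAP says the closest one. That it may fall after the visit is inferred from the absence of a stated direction.
- *That all endoscopic endpoints are equally at risk.* Two of them need a central reading.
- *That one patient moves the rate by 1/14 = 7.1 points.* The 14 are patients treated for more than 3 years as of 30 November 2021, not M48 attendees, and the shells of the proportion tables use the column N. Only the OC shift table for clinical remission (14.2.5.3) divides by non-missing observations, and the documents do not give that number at M48.
- *That the chance of the event can be computed.* At M12, 3 of 19 patients had no endoscopy, but sigmoidoscopy was not mandatory then and is at M48. In any case, a rate of missing endoscopies is not a rate of off-drug substitution.
- *That the same conflict exists at M24 and M36.* The bar on later endoscopy is specific to M48. At those visits the point applies only to a patient who has just stopped treatment.

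**Conclusion.** The gap is real and narrow. Followed as written, SAP 11.3 allows an M48 clinical remission to rest on an endoscopy done up to about 29 to 32 days after the last ABX464 dose, and it lets that result displace NRI non-response. Clinical response may be affected if a local reading can feed the MMS. Endoscopic improvement and remission are less exposed.

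The event is probably rare, and its frequency cannot be derived from the documents. Each reclassified patient is worth 4.5 points in the Total column of either set. The conclusion assumes a month of 28 to 31 days, 22 dosed patients, the denominators in the table shells, and the absence of any unstated direction or treatment condition in the rule.

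**What to change.** Add one condition to SAP 11.3, before database lock: a substitute endoscopy is used only if it falls within 1 month of the scheduled assessment and is dated no later than the day after the last ABX464-102 dose. For M48 this means on or before the visit. Otherwise the assessment is missing in the OC Set and non-response in the NRI Set. State how many days a month is.

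Do not restrict M48 substitutes to day -14 to day 0. Endoscopies between day -15 and the 1-month limit are on drug, and discarding them would create avoidable missing results and non-responders.

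In Listing 16.2.6.1, add the endoscopy date and a substitution flag, and list later endoscopies without using them for the endpoints.

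The cost is one sentence, one date comparison in the derivation and two listing columns. No study procedure changes. The downside is that an occasional patient becomes missing (OC) or a non-responder (NRI) at M48.

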### 11.3.1 Efficacy Variables

Descriptive statistics will be presented for all efficacy variables for each measurement timepoints. All efficacy data will be listed.

#### 11.3.1.1 Mayo Score

The **Total Mayo score** (TMS) consists of 4 items: stool frequency, rectal bleeding, flexible sigmoidoscopic examination, and a physician global assessment of disease activity (see protocol Appendix 3).

A non-invasive 9-point Mayo or **partial Mayo Score** (pMS) incorporates stool frequency, rectal bleeding, and the physician's global assessment of disease activity. The partial Mayo Score has been found to correlate closely with the full Mayo score and to independently have strong discriminative and construct validity and responsiveness to change in disease activity. Either the Partial or the Total Mayo score will be completed at each subject visit by the Investigator.

**Modified Mayo Score** (MMS) consists of 3 items: stool frequency, rectal bleeding, flexible sigmoidoscopic examination.

**Partial Modified Mayo Score** (pMMS) consists of only 2 items: stool frequency and rectal bleeding. MMS or pMMS will also be used in descriptive analysis and for efficacy evaluation.

Absolute values and change from BIS and from BOLS to each post BOLS timepoint will be presented using descriptive statistics for Total Mayo Score (TMS), Partial Mayo Score (pMS), Modified Mayo Score (MMS) and partial Modified Mayo Score (pMMS) (*Table 14.2.1.1 and 14.2.1.2*) and for the different components of the Total Mayo Score (stool frequency, rectal bleeding, physician rating of disease activity and mucosal appearance at endoscopy – central reading) (*Table 14.2.1.3 and 14.2.1.4*).

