1.3. Rationale for the clinical study and study design

Phase IIb study (ABX464-101) aimed at evaluating the efficacy and safety of ABX464 given at a fixed dose of 50mg once daily versus placebo in patients with moderate to severe active UC who have failed or are intolerant to immunomodulators, anti-TNF α or corticosteroids was conducted in Belgium, France, Germany, Austria, Poland, Hungary.

32 patients were randomized (23 ABX464 patients/9 placebo). The principal study results are presented below.

A strong efficacy signal was observed with ABX464 50 mg:

- Clinical Remission rate of 35.0 % of ABX464 patients (Placebo = 11.1%)
- Mucosal Healing rate of 50.0 % (p=0.03) of ABX464 patients (Placebo = 11.1%)
- Clinical Response rate of 70.0 % of ABX464 patients (Placebo = 33.0%)

Same results were also observed in Total and Partial Mayo Score, as depicted in the following graphs

[figure not shown]

Figure 3: Mean change in Total and Partial Mayo Score in ABX464-101 study

At the end of the completed 2 months induction treatment study, 22 Patients (15 previously treated with ABX464 and 7 on placebo) were enrolled into the open-label maintenance study with ABX464 50mg daily (ABX464-102) regardless of what treatment they had previously received. An interim analysis of this maintenance study was performed after all patients had completed at least 12 months dosing in the maintenance study, with a mean ABX464 treatment duration in the maintenance study of 422 days.

The interim analysis used the Month 12 Per Protocol (M12 PP) dataset which included all subjects that had a Month 12 visit. Of the 22 subjects, 3 subjects were excluded from the M12 PP Set: 2 subjects from the ABX464 induction group (one who withdrew due to lack of efficacy at M1 of the maintenance study and one who was lost to follow-up) and 1 subject from the placebo induction group (grade 2 headache at month 4), resulting in 19 subjects analyzed in the efficacy M12 PP set at baseline. Of the nineteen subjects in the set, sixteen had had a Month 12 endoscopy performed which forms part of the Total Mayo score (TMS).

Clinical remissions obtained at the end of the induction study were durable and the rates further improved during the maintenance phase, as additional subjects achieved clinical remission for 12 months treatment.

All patients who had an endoscopy performed, had an endoscopic sub-score of 0 or 1. 12/16 patients were in clinical remission at month 12.

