## 10.4 MISSING DATA

For missing continuous variables, Last Observation Carried Forward (LOCF) imputation method will be used for both the OC Set and the NRI Set. Missing dichotomous variables will not be imputed in the OC Set but will be imputed in the NRI Set as non-responder.

There will be no other imputation of missing data in this study.

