|                               | SD        | xx.xx  | xx.xx  | xx.xx           |
|                               | Minimum   | xx.x   | xx.x   | xx.x            |
|                               | Maximum   | xx.x   | xx.x   | xx.x            |
|                               | Median    | xx.xx  | xx.xx  | xx.xx           |
|                               | Quartiles | xx.xx – xx.xx                                      | xx.xx – xx.xx                                  | xx.xx – xx.xx   |
| BOLS                          | n         | xx (xx.x %)  | xx (xx.x %)                                    | xx (xx.x %)     |
|                               | Missing   | xx (xx.x %)  | xx (xx.x %)                                    | xx (xx.x %)     |
|                               | Etc       |  |  |                 |
| Change from BIS to BOLS       | n         | xx (xx.x %)  | xx (xx.x %)                                    | xx (xx.x %)     |
|                               | Mean      | xx.xx  | xx.xx  | xx.xx           |
|                               | Etc       |  |  |                 |
| Visit                         | n         | xx (xx.x %)  | xx (xx.x %)                                    | xx (xx.x %)     |
|                               | Missing   | xx (xx.x %)  | xx (xx.x %)                                    | xx (xx.x %)     |
|                               | Etc       |  |  |                 |
| Change from BIS to Visit      | n         | xx (xx.x %)  | xx (xx.x %)                                    | xx (xx.x %)     |
|                               | Mean      | xx.xx  | xx.xx  | xx.xx           |
|                               | Etc       |  |  |                 |

Version Date 20 MAY 2021

Template STATt004

Page 38 of 97

|                           |      |             |             |             |
|---------------------------|------|-------------|-------------|-------------|
| Change from BOLS to Visit | n    | xx (xx.x %) | xx (xx.x %) | xx (xx.x %) |
|                           | Mean | xx.xx       | xx.xx       | xx.xx       |
|                           | Etc  |             |             |             |

Etc

Partial Mayo Score (pMS)

Etc

Modified Mayo Score (MMS)\*

Etc

Partial Modified Mayo Score (pMMS)

Etc

---

\*Total Mayo Score and Modified Mayo Score are only collected at visits where an endoscopy is carried out.

The denominator for each percentage is the number of patients within the column.

BIS: Day 0 of ABX464-101 study

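### LOCF on the Total and Modified Mayo Scores can carry an old total into a visit without endoscopy and contradict the partial score observed that day

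*SAP*

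**What the plan says.** **Where the totals are summarised.** SAP 11.3.1.1: "Absolute values and change from BIS and from BOLS to each post BOLS timepoint will be presented using descriptive statistics for Total Mayo Score (TMS". The same sentence covers the partial score (pMS), MMS and the partial modified score (pMMS). The parent section, 11.3.1, is worded more narrowly: "Descriptive statistics will be presented for all efficacy variables for each measurement timepoints".

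**How missing values are handled.** SAP 10.4: "For missing continuous variables, Last Observation Carried Forward (LOCF) imputation method will be used for both the OC Set and the NRI Set", followed by "There will be no other imputation of missing data in this study". SAP 6.1 and 6.2 repeat LOCF for continuous values. For dichotomous values, 6.1 allows no imputation and 6.2 counts a missing value as non-response.

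**Where the totals exist.** The footnote to shell Table 14.2.1.1 reads: "Total Mayo Score and Modified Mayo Score are only collected at visits where an endoscopy is carried out". Protocol 5.3.9 makes sigmoidoscopy mandatory at D56/M2, M24, M36 and M48, with optional monthly procedures up to M24. Some form of the score is available at every visit: "Either the Partial or the Total Mayo score will be completed at each subject visit by the Investigator".

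**M12.** Protocol 5.3.10 and SAP 11.3.1.6 assess remission and response at M12, where the current protocol mandates no endoscopy. Protocol 1.3 reports that 19 patients had an M12 visit, of whom "sixteen had had a Month 12 endoscopy performed which forms part of the Total Mayo score".

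**Response.** SAP 11.3.1.6 builds clinical response on MMS: "reduction in Modified Mayo Score of at least 2 points and" at least 30 percent from the induction baseline, plus a rectal bleeding condition.

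**The concern.** TMS is pMS plus one endoscopy item scored 0 to 3; MMS is pMMS plus the same item. When a patient attends without endoscopy, only that one item is unknown. Carrying the whole total sets aside the items observed that day and puts in their place a sum from an earlier date. A patient who has since improved keeps a high total, and one who has since relapsed keeps a low one.

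Change in TMS is a listed secondary endpoint, and M12 is a named timepoint for remission and response. With about 20 patients, a few such values can move a summary. There is also a knock-on risk for a dichotomous endpoint: a carried MMS could supply a response result at a visit where the SAP's own rules call for a missing value or non-response.

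**Working it through.** The plan states no figure on this point, so there is nothing to reproduce. The check is a visit count and exact score arithmetic.

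**1. Visits (Protocol 5.1 and 5.2).** D7, D14, D21, D28, D42 and D56/M2 make 6. M3 to M24 monthly adds 22, M27 to M45 quarterly adds 7, M48 adds 1 and EoS adds 1: 6 + 22 + 7 + 1 + 1 = 37. Endoscopy is mandatory at 4, so 37 − 4 = 33 visits have none mandated. M12 is one of the 33.

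**2. Possible range.** With endoscopy item E from 0 to 3, pMS ≤ TMS ≤ pMS + 3. Likewise pMMS ≤ MMS ≤ pMMS + 3.

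**3. When a carried total stays possible.** The carried total is P_prev + E_prev. It is possible today only if 0 ≤ P_prev + E_prev − P_now ≤ 3. Rearranged: E_prev − 3 ≤ P_now − P_prev ≤ E_prev.

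| Last endoscopy item | Change in partial score that keeps the carried total possible |
|---|---|
| 0 | −3 to 0 |
| 1 | −2 to +1 |
| 2 | −1 to +2 |
| 3 | 0 to +3 |

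Protocol 1.3 reports that every patient with an M12 endoscopy scored 0 or 1. After such a result, a rise of 1 point (item 0) or 2 points (item 1) in the partial score puts the carried total below the partial score.

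**4. Hypothetical examples.**

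| Last pMS + endoscopy | pMS today | Carried TMS | Endoscopy item implied | Possible TMS today | Today's pMS + last endoscopy item |
|---|---|---|---|---|---|
| 1 + 1 | 4 | 2 | −2 | 4 to 7 | 5 |
| 6 + 3 | 1 | 9 | 8 | 1 to 4 | 4 |
| 2 + 1 | 2 | 3 | 1 | 2 to 5 | 3 |

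The first two carried totals are impossible and the third is not. The last column always lies in range, because the implied item is then E_prev itself.

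**5. Relapse.** Protocol 7.2 defines the partial-score part of UC worsening as a 2-point rise in pMMS to at least 4. Counting from the last endoscopy visit, 12 pairs of earlier and current pMMS show a rise of at least 2 to at least 4. The carried MMS is impossible in 12 of 12 pairs when the last endoscopy item is 0, 12 of 12 when it is 1, 9 of 12 when it is 2 and 6 of 12 when it is 3. These are counts of score combinations, not patient frequencies.

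**6. M12 and response.** 19 − 16 = 3 attending patients had no endoscopy. If MMS is carried first and response derived second, up to 3 patients receive a response value that should be missing under 6.1 and non-response under 6.2. Taking all 22 enrolled patients as the NRI denominator (this assumes that all were dosed), that is at most 3/22 = 13.6 percentage points.

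**The case against.** The strongest reply is that the SAP never says LOCF acts on the whole score, nor that a total which was not due at a visit counts as missing. Section 11.3.1 limits summaries to timepoints of measurement, the shell footnote ties TMS and MMS to endoscopy visits, and the shell keeps a row for missing values. The broad wording in 11.3.1.1 sits in a sentence that also covers pMS and pMMS, which can be scored at every visit. A reader might infer that the plan prescribes carried totals at all 33 visits without mandated endoscopy, or that impossible totals must follow. The documents do not support either: whole-score carrying is the literal reading but is not stated, and a carried total stays possible when the partial score changes little.

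That reply stands as to extent, but it does not remove the problem. Neither the narrower wording nor the footnote switches LOCF off. M12 remains a named timepoint without mandatory endoscopy. Optional endoscopies make other months measurement timepoints for some patients only. A missed endoscopy at a mandatory visit raises the same question. The one-month substitution in SAP 11.3 covers a scheduled endoscopy, and the current protocol schedules none at M12.

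It is also fair to say that the clash with 6.1 and 6.2 depends on an order of derivation that the SAP leaves open, and that remission is defined from sub-scores, so a carried total alone does not alter it. Finally, the partial scores and components are tabulated and listed separately, so a careful reader could detect a mismatch. That makes the fault visible; it does not make the TMS and MMS summaries right.

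**Conclusion.** The concern holds in a limited form. Taken together, 10.4 and 11.3.1.1 allow an old TMS or MMS to stand at a visit where all items except endoscopy were observed, and the carried value can be impossible given those items. The bound is exact. It needs a partial score recorded that day, so it does not concern patients who have left the study.

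The frequency cannot be computed, because the documents give no patient-level scores. A reader might put about 0.6 points on the M12 mean TMS. That needs all three patients without endoscopy to be wrong by 4 points in the same direction (3 × 4 / 19 = 0.63), which nothing in the documents shows. With an assumed common error of 1 to 4 points, the shift would run from 0.16 to 0.63.

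A reader might also count 6 of 22 patients as exposed to a wrong response value at M12 (22 − 16). Three of those six were outside the M12 set: one withdrew at M1, one was lost to follow-up and one was excluded with a headache at month 4. They have no M12 items to contradict. The figure for attending patients is at most 3, and only if LOCF precedes the derivation of response.

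The outputs are descriptive secondary summaries. The primary endpoint is treatment-emergent adverse events, and no error rate or sample size is affected. The point still deserves correction before database lock, because programmers following the same text could produce different tables.

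**What to change.** In SAP 10.4 and 11.3.1.1:

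1. Exempt TMS, MMS and the endoscopy item from LOCF.
2. Summarise these three only from visits where endoscopy was done, and show the rest as missing. Include optional endoscopies and the one-month substitute, and extend that substitution to M12. Restricting the tables to a fixed list of visits would instead drop totals observed at optional endoscopies, which Protocol 5.3.9 has entered in the eCRF.
3. Optionally, add a sensitivity table that combines the last endoscopy item with the items observed that day. This cannot produce an impossible total.
4. State in 11.3.1.6 that response and remission are derived from observed components first, and that the non-responder rule of 6.2 is applied afterwards.

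The cost is a few sentences and some programming, with no new data. The downside is a smaller n for TMS and MMS at some visits; pMS and pMMS still cover visits without endoscopy.
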